### **15.2.2 Statistical Analysis on PK Parameters**

Serum concentrations will be listed and summarised by time point. The PK parameters will be listed for each subject and summarised for each treatment group using descriptive statistics (N - the number of subjects, arithmetic mean, SD - standard deviation, CV - coefficient of variation, geometric mean, median, minimum, maximum).

Analysis of variance models will be applied to the dose normalised and logarithmically transformed pharmacokinetic parameters to investigate possible deviations from dose proportionality.

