**Part B:**

Group 3: 0.5 mg/kg i.v. loading dose and 0.03 mg/kg/h maintenance dose i.v. over 7 hours and 45 min;

Group 4: 1 mg/kg i.v. loading dose and 0.1 mg/kg/h maintenance dose i.v. over 7 hours and 45 min;

Group 5: 2 mg/kg i.v. loading dose and 0.3 mg/kg/h maintenance dose i.v. over 7 hours and 45 min;

Group 6: 5 mg/kg i.v. loading dose and 1 mg/kg/h maintenance dose i.v. over 7 hours and 45 min;

Group 7: 5 mg/kg i.v. loading dose and 3 mg/kg/h maintenance dose i.v. over 7 hours and 45 min;

Group 8: 5 mg/kg i.v. loading dose and 9 mg/kg/h maintenance dose i.v. over 7 hours and 45 min.

Please refer to Table 1.

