#### **Pharmacokinetics:**

Individual and mean concentration versus time will be plotted on linear and semi logarithmic scales. Plasma concentrations and plasma PK parameters will be listed for LR12. Summary statistics of PK parameters including means, geometric means, medians, ranges, standard deviations, coefficients of variation will be presented for each dose.

Analysis of variance models will be applied to the dose normalised and logarithmically transformed pharmacokinetic parameters to investigate possible deviations from dose proportionality

---

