**Table 1. Adaptive Protocol Features.**

Adaptive Study Design Areas	Features	Limits
Dose	
 
1. All anticipated dose levels/dosing regimens in Parts A and B can be adjusted in accordance with PK, safety and tolerability data collected up to the decision making time-point.
 
2. In Part B, the anticipated dosing regimens can be adjusted in accordance with PK, safety and tolerability data collected up to the decision making time-point.
 
3. The term dosing regimen includes (1) the dose level administered as loading dose, (2) the dose level administered as maintenance dose (3) the duration of the loading dose and (4) the duration of the maintenance dose. Accordingly, these can be adjusted individually or in combination.
 
	
 
I. The starting dose for Part A of the study will not exceed 1 mg.
 
II. The maximum dose for Part A will not exceed 10 mg.
 
III. The starting loading dose in Part B will not exceed 0.5mg/kg.
 
IV. The starting maintenance dose in Part B will not exceed 0.03 mg/kg/h.
 
V. The dose increments between the dose levels 1 to 2 in Part A will be no more than 10-fold.
 
VI. The loading dose increments between the dose levels in Part B will be no more than 2.5-fold.
 
VII. The maintenance dose increments between the dose levels in Part B will be no more than 3.5-fold.
 

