**Table 3. Study Plan – Part B (Groups 3 to 8).**

Groups 3 to 8	Screening		Assessment Period												FU Visit	EOS Visit
	D-14 to D-2	D-1	Predose	H0	H1	H2	H3	H4	H5	H6	H7	H8	H10	H24		
	D1												D2	D8±1	D28±2	
SCREENING PROCEDURES																
Signature of the informed consent	X															
Medical history	X	X														
Prior medications	X	X														
Physical examination	X	X 												X 	X 	X 
Viral Serology	X															
Alcohol breath test & Urine Drug Screen	X	X														
Inclusion / exclusion criteria	X	X														
Randomisation				X												
24h Holter	X															
Hospitalisation																
Study treatment schedule				i.v. loading dose T0 to T15'												
Meals 		X										X			X	
SAFETY ASSESSMENTS																
Vital signs  (including BMI assessment at screening)	X	X	X	T0', T10', T20, T30, T40, T50'	X	X	X	X	X	X	X	X	X	X	X	X
ECG	X	X	X	T15'	X								X	X	X	
Telemetry 			X													
Haematology	X	X		T15'				X							X	
Coagulation	X	X		T15'				X							X	
Serum chemistry	X	X		T15'				X							X	
Urinalysis	X	X													X	
Infusion site assessment			X	T15' (6)	X	X		X		X		X			X	
Anti-LR12 antibody screening 			X												X	X
Pharmacokinetics 			X	T5', T15', T18', T30', T45'	X	X		X		X			T-15, T2', T4', T7', T15', T30	X		
Adverse Events	←														→	
Concomitant medication	←														→	

(1) Brief physical examination.

(2) Standard meals will be served at standard times. Meal at dismissal will be optional.

(3) Time of procedures is relative to the start of infusion.

(4) Tympanic temperature will be collected at pre-dose and at H8 only. Vital signs at H0 and H8 will be measured only in supine position.

(5) 12-Lead telemetry will be recorded from pre-dose to 10 h post-dose.

(6) The check of the local tolerability at H0 should be performed just after the loading infusion.

(7) PK sampling performed at the end of the 8 hours i.v. infusion will be as follows: 15 min before H8 (T-15'), then during 30 min after the end of the infusion as specified in the table. H0 timings refer to start of infusion.

---

(8) Should any subject develop ADA against LR12, they will be followed up for at least 3 months or until the antibody response is no longer detected.

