**Table 8. Planned Dose Escalation Scheme.**

Group	Loading dose			Maintenance dose		
	(mg/kg) 15 min	Rate (mg/kg/h)	Total (mg)*	Rate (mg/kg/h)	Total 7h45 (mg/kg)	Total 7h45 (mg)*
1	0.014	0.057	1	-	-	-
2	0.140	0.570	10	-	-	-
3	0.500	2.000	35	0.03	0.23	16.3
4	1.000	4.000	70	0.10	0.78	54.3
5	2.000	8.000	140	0.30	2.33	162.8
6	5.000	20.000	350	1.00	7.75	542.5
7	5.000	20.000	350	3.00	23.25	1,627.5
8	5.000	20.000	350	9.00	69.75	4,882.5

\*Assuming a body weight of 70kg

The second dose planned to be administered to humans is 10 mg as a “loading” dose infused i.v. for 15 minutes. This will be equivalent to a rate of infusion of 0.57 mg/kg/h and to 0.14 mg/kg dose for an individual of 70 kg.

According to this, the second cohort dose rate in mg/kg/h will be 3.3 times lower than the NOAEL HED BS (1.88 versus 0.57) and 10 times lower than the NOAEL HED BW (5.83 versus 0.57). In terms of total exposure, knowing that the reference taken in toxicology studies is of 24 hours and that total exposure time for this cohort will be 15 minutes, the total exposure in a one-day period in mg/kg will be 323 times lower on the basis of HED BS (45.16 versus 0.14) and 1000 times lower on the basis of HED BW (140 versus 0.14).

If the highest loading dose given during the toxicology study is considered, the second cohort dose in mg/kg/h will receive a 45 times lower dose by HED BS conversion (25.81 versus 0.57) and a 140 times lower dose according to HED BW (80 versus 0.57). The total exposure in a 15 minutes period in mg/kg will be 46 times lower on the basis of HED BS (6.45 versus 0.14) and 143 times lower on the basis of HED BW (20 versus 0.14).

From cohorts 3 to 6, the loading dose will be increased incrementally by a factor 2 (or 2.50).

The first maintenance dose rate will be introduced in cohort 3 and is of 16.3 mg at an infusion rate of 0.03 mg/kg/h for a total exposure time of 7h45. This corresponds to 0.23 mg/kg dose for an individual of 70 kg.

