#### **Cmax and tmax**

Cmax : Maximal plasma concentration  
tmax : Time at which the maximum plasma concentration occurs  
C0.25h : Concentration at the end of the loading infusion  
C8h : Concentration at the end of the maintenance infusion  
Css inf : Steady state concentration during the maintenance infusion

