**Reason for Amendment:**

1. The purpose of this amendment is to adjust the maintenance dose increment between cohort 7 and cohort 8 to a factor of 2. The amendment describes the administration of a 6 mg/kg/h maintenance dose to cohort 8 in line with Adaptive Feature number 1, limit VII, Adaptive Features 2 and 3 Limits I and III.

The current approved protocol for the study MOT-C-104 (version 3.0 dated 13 May 2016) foresees an increment of 3 for the maintenance dose in all cohorts of Part B and progression to the maintenance dose of 9 mg/kg/h (over 7 hours and 45 minutes) in cohort 8.

Since the dose of 9 mg/kg/h is not planned for therapeutic use and was only foreseen to document the safety of the product, a reduced maintenance dose of 6 mg/kg/h is considered sufficient for documenting the safety of the product in healthy volunteers considering the currently available data. The Safety Review Committee agreed to escalate to the cohort 8 with an increment of 2 rather than 3 and thus give 6 mg/kg/h for 7 hours 45 minutes.

These changes will not affect the volunteers' safety.

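### Section 15.2.2 tests dose proportionality by ANOVA but states no estimate of the size of a departure; adding a power-model slope with its 90% CI is a cheap improvement of modest weight

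*Combined protocol and SAP*

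**What the plan says.** Section 15.2.2 states: "Analysis of variance models will be applied to the dose normalised and logarithmically transformed pharmacokinetic parameters to investigate possible deviations from dose proportionality". The synopsis plans the same analysis; its wording begins "Analysis of variance models will be applied to the dose normalised and logarithmically transformed pharmacokinetic parameters". Neither names the dose used for normalisation, the parameters analysed, a contrast, an interval or a criterion.

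A Part B regimen has more than one dose. Table 1 states: "The term dosing regimen includes (1) the dose level administered as loading dose, (2) the dose level administered as maintenance dose". The lowest Part B regimen is "Group 3: 0.5 mg/kg i.v. loading dose and 0.03 mg/kg/h maintenance dose i.v. over 7 hours and 45 min". By Table 8 the loading dose stops rising at Group 6, while the maintenance rate continues to rise. Amendment 4 then changes the top step: "The purpose of this amendment is to adjust the maintenance dose increment between cohort 7 and cohort 8 to a factor of 2", that is, to 6 mg/kg/h.

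Section 15.2.1 defines Css inf as "Steady state concentration during the maintenance infusion", with no sampling window. It also lists clearance for each subject. Section 15.4 reports no power calculation and mostly descriptive statistics. Section 15.1 announces a statistical analysis plan to be agreed by the sponsor; its text is not among the documents.

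**The concern.** The plan sets out to investigate departures from proportionality. The useful answer is a size with its precision: by what factor does exposure fall short of, or exceed, what the dose predicts? Section 6.3 says the data will help to design patient studies, and a p-value from a six-group comparison of three subjects each does little for that. A significant result would not say how large the departure is. A non-significant one would say little, because an omnibus test spreads its power over five degrees of freedom when the plausible departure is a trend.

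Two details bear on any such estimate. The loading dose, maintenance rate and total dose rise by very different factors, so the dose has to be matched to the parameter. And Css inf needs samples from which the loading dose has cleared.

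**Working it through.** **Plan's own figures.** Table 8 reproduces. Group 3: 0.03 × 7.75 h = 0.2325 mg/kg, × 70 kg = 16.3 mg. Group 8: 9 × 7.75 = 69.75 mg/kg, × 70 = 4,882.5 mg.

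**Dose ranges, Groups 3 to 8.** Total = loading + 7.75 × rate.
- Loading: 0.5, 1, 2, 5, 5, 5 mg/kg; 10-fold.
- Rate: 0.03, 0.1, 0.3, 1, 3, then 6 mg/kg/h (Amendment 4); 200-fold (300-fold at 9).
- Total: 0.7325, 1.775, 4.325, 12.75, 28.25, 51.5 mg/kg; 70-fold (74.75 mg/kg and 102-fold at 9).

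**Assumptions.** The documents give no CV, effect size or level. I take a log-normal CV of 30% (range 20–40%), a 5% test and a true slope of 0.9. Over 200-fold, 200^−0.1 = 0.59, so the top group lies 41% below proportional relative to the lowest.

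**Power.** σ = √ln(1 + CV²) = 0.2936 at 30%. Sxx is the sum of squares of ln(dose) over the six groups: 20.63 for rate, 13.50 for total. For a log-linear departure all three tests share the noncentrality 3·Sxx·(b − 1)²/σ², which is 3 × 20.63 × 0.01/0.0862 = 7.18 for Css and 4.70 for AUC. Only the degrees of freedom differ.

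| CV | Parameter | Omnibus (5,12 df) | Trend contrast (1,12) | Slope (1,16) |
|---|---|---|---|---|
| 20% | Css | 69% | 95% | 96% |
| 30% | Css | 34% | 69% | 71% |
| 40% | Css | 21% | 47% | 48% |
| 30% | AUC | 23% | 51% | 53% |

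At 9 mg/kg/h and 30% CV, the Css omnibus and slope figures are 38% and 75%.

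**Precision.** The 90% CI half-width for b is t(0.95, 16)·σ/√(3·Sxx). For Css this is 1.746 × 0.2936/√61.9 = 0.065 (0.044 to 0.085 at 20–40% CV). For AUC it is 0.081 and for C0.25h on loading dose 0.13. The trend contrast in the ANOVA gives 0.0665 for Css. Over the whole range, 0.065 corresponds to 200^0.065 = 1.41-fold either way. A plain Group 8 v Group 3 contrast gives exp(1.782 × 0.2936 × √(2/3)) = 1.53-fold.

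**What a slope can miss.** Suppose one group is off 2-fold at 30% CV. The omnibus noncentrality is 3 × (ln 2)² × (5/6)/0.0862 = 13.9, giving 63% power whichever group it is. By simulation (40,000 trials) the slope test on the rate axis detects it 50, 12, 2, 2, 15 and 37% of the time for Groups 3 to 8. If ANOVA and slope were both read as 5% tests, at least one would be significant under exact proportionality in about 9% of trials.

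**Css inf window.** I assume one-compartment linear PK, a 15-min load then a constant rate, 6 mg/kg/h in Group 8, and true b = 1. Samples during the infusion are read as H1, H2, H4, H6 and 7 h 45 (the Table 3 row is broken in the copy available). All half-lives are assumed.

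| Half-life | b, H1 only | b, H2 only | b, average of all five | b, 7 h 45 only |
|---|---|---|---|---|
| 5 min | 0.98 | 1.00 | 0.996 | 1.00 |
| 10 min | 0.82 | 0.995 | 0.94 | 1.00 |
| 15 min | 0.72 | 0.96 | 0.89 | 1.00 |
| 30 min | 0.63 | 0.82 | 0.82 | 1.00 |
| 60 min | 0.59 | 0.72 | 0.79 | 0.99 |

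The mechanism is residue from loading in the low groups. At a 30-min half-life and H2, Group 3 reads 2.64 times its true Css and Group 8 reads 1.00 times.

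**The case against.** The best defence is that section 15.2.2 says analysis of variance models and does not limit itself to an omnibus F test. A trend contrast in that framework matches the slope to within two points of power and 0.0015 in half-width, and ANOVA on log values also yields geometric mean ratios with intervals. This stands. The power model is not a large statistical gain. What is missing is a commitment to report any estimate at all.

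Clearance is listed by subject and summarised by group, so proportionality of AUC to total dose will be visible descriptively. That also stands, but it does not cover C0.25h or Css inf and carries no stated interval. The announced analysis plan may settle the dose, contrasts and window, and this cannot be checked.

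Three stronger inferences are tempting and are not supported:
- **That the plan divides by the wrong dose.** Under exact proportionality, an omnibus test of Css inf divided by total dose would reject 91% of the time at 30% CV and 6 mg/kg/h. But no passage plans such a mismatch, the listed parameters separate the dose components, and ANOVA on matched doses is valid. The unnamed dose is missing detail.
- **That Css inf will be contaminated by the loading dose.** The definition itself says steady state, so using samples taken before steady state would contradict it. At a 5-min half-life the bias almost vanishes.
- **That non-linearity is already shown.** Section 6.4.2.1 describes dose-dependent kinetics in monkeys, which may mean only that exposure rises with dose. Its 15 to 30 minutes is not stated to be a half-life.

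**Conclusion.** The point holds as a cheap improvement of modest weight. The plan asks a proportionality question without stating an estimate of the answer, and an omnibus six-group reading would be weak against a trend: 34% power for Css inf, against 71% for a slope and 69% for a trend contrast. A 90% CI of about ±0.065 on the Css slope is attainable from the planned 18 active subjects. These figures rest on the assumed slope of 0.9, 30% CV, 5% level and 6 mg/kg/h in Group 8.

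The sampling rules for Css inf and C8h are clarifications, not errors. In the linear model, early samples bias b appreciably only if the half-life is about 10 minutes or longer, and no human half-life is given. The analysis is secondary, and these calculations do not bear on dose escalation.

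**What to change.** In section 15.2.2 or the statistical analysis plan:

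- Keep the planned ANOVA on matched dose-normalised log values.
- Add, on Part B active subjects, ln(parameter) = a + b·ln(dose). Report b with its 90% CI as an estimate, not as a second test.
- Name the dose: loading dose for C0.25h and AUC(0-0.25h); maintenance rate for Css inf and C8h; total mg/kg actually given, from the dosing records, for AUC(0-8h), AUC(0-t) and AUC(0-inf).
- Describe Cmax only. Do not dose-normalise CL, Vd, t1/2, λz or tmax.
- Take Css inf from late-infusion samples: the one 15 minutes before H8 (Table 3, footnote 7), with H6 if the table row is read correctly.
- State which sample supplies C8h, since footnote 7 lists none at H8 itself.

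The cost is a paragraph of wording, with the same subjects and samples. The slope assumes log-linearity and can miss a single aberrant group, which is why the ANOVA stays. Even under linear PK, AUC(0-8h) on total dose gives b slightly below 1 (0.994, 0.987 and 0.973 at assumed half-lives of 15, 30 and 60 minutes), so small departures there should not be over-read.

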### **15.3 Handling of Missing and Incomplete Data**

Unrecorded values will be treated as missing. The appropriateness of the method(s) for handling missing data will be reassessed at the data review prior to database lock. Depending on the extent of missing values, further investigation may be carried out into the sensitivity of the analysis results to the method(s) specified.

### **15.4 Determination of Sample Size**

The sample size is based on experience from previous similar Phase I studies. No formal power calculation has been performed and mostly descriptive statistics will be used to summarise safety, pharmacokinetic and pharmacodynamics data.

### **15.5 Interim Analysis**

One interim analysis of safety and PK data is planned, after the treatment phase (Day 2) of cohort 6 is complete. Details will be specified in a separate statistical analysis plan.”

## **16 DATA MANAGEMENT**

Data Management will create the database under Oracle (V10.2.04 or higher) and the e-CRF entry screens using Clinsight Ennov Clinical © (V7 or higher) in compliance with the e-CRF design.

The e-CRF application will be accessible by connecting on a dedicated and secure website using Clinsight Online module. Each user will connect by using personal identifier / password.

The Data Manager will write the Data Handling Manual (DHM) which describes the various data management steps, the database structure (name and format of the items) and the annotated e-CRF, and the validation plan.

The investigator, sub-investigators or its designated representative will enter the data for each subject on the Ennov Clinical Online e-CRF application. The data will be extracted from the ORACLE database and formatted as SAS files (V9.4) using Ennov Clinical Export module.

The Data Manager will program the consistency checks defined in the validation plan using Ennov Clinical Test module. These checks will result in the production of Electronic Data Clarification Forms (e-DCFs). The investigator, sub-investigator or its designated representative will directly answer to these e-DCFs on the e-CRF application.

Adverse events will be coded using MedDRA dictionary, and concomitant treatment will be coded using WHO-DRUG dictionary version 2015-3 or higher.

At the end of the validation process, the Data Manager will produce listings which describe all protocol deviations. The status of these deviations (minor or major) will be discussed during the pre-analysis review, and the analysis population will be defined.

At the end of the data management process, the database will be frozen and the SAS files will be sent to INOTREM SA according to the Data transfer process.

## **16.1 Case Report Forms**

The e-CRF will be available online, on a secure website (<https://ecrf.novasco.fr/CSOnline/>). Only the investigators, or the sub-investigators/designee, are authorised to entry data in the e-CRF. They are identified using a login and a password as an electronic signature. At the beginning of the study, a login will be allocated to each site staff who will be asked to identify himself/herself by a personal password.

The investigator, the sub-investigator or its designated representative will create a new e-CRF for each subject having signed the informed consent and randomised. Any additional information on data entry process will be included in the DHP. The investigator must check that all the data is accurate and correct. If any information is not applicable, missing (not determined) or unknown, the investigator will record "NA", "ND" or "UK" in the appropriate place. After a page/screen is completed, the investigator has to validate it (lock action). This action prevents from modification of the data after entry (data are "frozen").

If a data that has already been validated in the e-CRF has to be corrected, the initial value, the identity of the person who modify the data, the date and the reason of the modification are tracked in an audit trial file, linked to the e-CRF, not accessible/not modifiable to/by the investigators. When, the correction is done; the investigator has to validate it.

Each opened case report form must be completed. After final verification by the monitor and resolution of possible queries, the data are definitively not modifiable by the investigator.

# **17 SPONSOR'S AND INVESTIGATOR'S RESPONSIBILITIES**

## **17.1 Sponsor's Responsibilities**

In addition to the responsibilities described in the below sections the Sponsor is responsible to inform the PI of any safety update relating to the IMP.

### **17.1.1 GCP Compliance**

INOTREM SA and any third party to whom aspects of the study management or monitoring have been delegated will undertake their roles for this study in compliance with all applicable regulations and ICH GCP Guidelines.

Visits to the Investigator site will be conducted by representatives of INOTREM SA to inspect study data, subjects' medical records, and CRFs in accordance with current GCP and the respective local and national government regulations and guidelines. Records and data may additionally be reviewed by auditors or by competent authorities.

### **17.1.2 Regulatory Approval**

INOTREM SA will ensure that Local Competent Authority requirements are met before the start of the study.

### **17.1.3 Indemnity/Liability and Insurance**

INOTREM SA will adhere to the recommendations of the Association of British Pharmaceutical Industry (ABPI) Guidelines. A copy of the Indemnity document will be supplied to the Investigator before study initiation.

INOTREM SA will ensure that suitable insurance cover is in place prior to the start of the study. An insurance certificate and a statement of insurance will be supplied to RPL.

### **17.1.4 Protocol Management**

All protocols and amendments will be prepared by INOTREM SA and/or RPL. If it becomes necessary to issue a protocol amendment during the course of the study, INOTREM SA will notify the Investigator and collect documented Investigator Agreement to the amendment.

